#### Cohort A Induction Study and Cohort B Induction Study

A summary of subject disposition will be provided by treatment group and overall for each individual Induction study. This summary will present the number of subjects screened, the number of subjects who met all eligibility criteria but were not randomized with reasons subjects were not randomized, the number of subjects randomized, and the number of subjects in each of the categories listed below:

- Full Analysis Set
- Safety Analysis Set
- PK Analysis Set
- PK Substudy Analysis Set
- CCI

- Completed study drug dosing through Week 10 (indicated in Induction Study Drug Completion eCRF)
- Continuing study drug (for analysis other than the final analysis)
- Did not complete study drug up to Week 10 with reasons for premature discontinuation of study drug
- Completed Induction Study through Week 11
- Continuing Induction Study (for analysis other than the final analysis)
- Did not complete Induction Study with reasons for premature discontinuation from the study

### Maintenance Study

A summary of subject disposition will be provided by treatment group and overall. This summary will present the number of subjects who completed the Induction Studies, the number of subjects re-randomized, and the number of subjects in each of the categories listed below:

- Full Analysis Set
- Safety Analysis Set
- PK Analysis Set
- **CCI**
- Completed study drug dosing through Week 58
- Did not complete study drug with reasons for premature discontinuation of study drug as captured in the CRF.
- Completed Maintenance Study (defined as completion of protocol-planned duration of the study through Week 58)
- Did not complete Maintenance Study with reasons for premature discontinuation from the study

For the status of study drug and study completion and reasons for premature discontinuation, the number and percentage of subjects in each category will be provided. The denominator for the percentage calculation will be the total number of subjects in the Safety Analysis Set corresponding to that column in that study.

A similar summary as described for subject disposition summary will be provided for discontinuing study drug or study due to COVID-19.

The following by-subject listings will be provided by subject identification (ID) number in ascending order to support the above summary tables:

- Reasons for premature study drug or study discontinuation (a separate listing of reasons for premature study drug or study discontinuation due to COVID-19 will be created)
- Reasons for screen failure (will be provided by screening ID number in ascending order)
- Lot number and kit ID of assigned study medication

#### **4.2. Extent of Study Drug Exposure and Adherence**

Extent of exposure to study drug will be examined by assessing the total duration of exposure to study drug and the level of adherence to the study drug specified in the protocol.

Summaries of extent of study drug exposure and adherence will be provided for:

- Cohort A Induction Study
- Cohort B Induction Study
- Maintenance Study

A by-subject listing will be provided to support summaries.

In addition, a by-subject listing of study drug administration will be created for subjects with study drug interruption due to COVID-19 impact.

##### **4.2.1. Duration of Exposure to Study Drug**

Total duration of exposure to study drug will be defined as last dosing date minus first dosing date plus 1, regardless of any temporary interruptions in study drug administration, and will be expressed in weeks using up to 1 decimal place (eg, 4.5 weeks). If the last study drug dosing date is missing (for subjects that have stopped treatment or the study as indicated by a study disposition record), the latest date among the treatment (study) disposition, clinical visit date, laboratory sample collection date, and vital sign assessment date that occurred during the on-treatment period (e.g. after exposure start date) will be used.

If month and year of the last dose are known, and the last study drug dosing date imputed above is different from the month collected, the last date of that month will be used. If only year of the last dose is known, and the last study drug dosing date imputed above is after the year collected, the last date of that year will be used; if the last study drug dosing date imputed above is before the year collected, the first date of that year will be used.

The total duration of exposure to study drug will be summarized for the following using descriptive statistics and using the number (ie, cumulative counts) and percentage of subjects exposed through the following time periods:

- Cohort A Induction Study: 1 day, 2 weeks, 4 weeks, 6 weeks, 10 weeks, and 11 weeks

- Cohort B Induction Study: 1 day, 2 weeks, 4 weeks, 6 weeks, 10 weeks, and 11 weeks
- Maintenance Study: 1 day, 3 weeks, 9 weeks, 15 weeks, 23 weeks, 31 weeks, 39 weeks, and 47 weeks

Summaries will be provided by treatment group for the Safety Analysis Set.

No formal statistical testing is planned.

#### **4.2.2. Adherence to Study Drug**

The total number of tablets administered will be summarized using descriptive statistics.

The presumed total number of tablets administered to a subject will be determined by the data collected on the drug accountability eCRF using the following formula. If the bottle was not returned, it is assumed that the subject took all the study drug tablets from the dispensed bottle. The number of tablets returned will be imputed as zero for the given bottle for study drug adherence calculation purpose.

The total number of tablets administered =

$$\text{Total number of tables dispensed} - \text{total number of tablets returned}$$

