### **5.2.2. Packaging and Labeling**

Filgotinib and PTM filgotinib tablets are packaged in white, high density polyethylene (HDPE) bottles. Each bottle contains 30 tablets, silica gel desiccant and polyester packing material. Each bottle is enclosed with a white, continuous thread, child-resistant polypropylene screw cap fitted with an induction-sealed, aluminum-faced liner.

Study drugs to be distributed to centers in the US, EU and other participating countries shall be labeled to meet applicable requirements of the US FDA, EU Guideline to Good Manufacturing Practice - Annex 13 (Investigational Medicinal Products), and/or other local regulations, as applicable.

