## **7.7. Special Situations Reports**

### **7.7.1. Definitions of Special Situations**

Special situation reports include all reports of medication error, abuse, misuse, overdose, occupational exposure, drug interactions, exposure via breastfeeding, unexpected benefit, transmission of infectious agents via the product, product complaints, counterfeit of falsified medicine, and pregnancy reports regardless of an associated AE.

Medication error is any unintentional error in the prescribing, dispensing, preparation for administration, or administration of an investigational product while the medication is in the control of the health care professional, patient, or consumer. Medication errors may be classified as a medication error without an AE, which includes situations of missed dose; medication error with an AE; intercepted medication error; or potential medication error.

Abuse is defined as persistent or sporadic intentional excessive use of an investigational product by a subject.

Misuse is defined as any intentional and inappropriate use of an investigational product that is not in accordance with the protocol instructions or the local prescribing information.

An overdose is defined as an accidental or intentional administration of a quantity of an investigational product given per administration or cumulatively which is above the maximum recommended dose as per protocol or in the product labelling (as it applies to the daily dose of the subject in question). In cases of a discrepancy in drug accountability, overdose will be established only when it is clear that the subject has taken the excess dose(s). Overdose cannot be established when the subject cannot account for the discrepancy except in cases in which the investigator has reason to suspect that the subject has taken the additional dose(s).

Occupational exposure is defined as exposure to an investigational product as a result of one's professional or non-professional occupation.

Drug interaction is defined as any drug/drug, drug/food, or drug/device interaction.

Unexpected benefit is defined as an unintended therapeutic effect where the results are judged to be desirable and beneficial.

Transmission of infectious agents is defined as any suspected transmission of an infected agent through an investigational product.

Product complaint is defined as complaints arising from potential deviations in the manufacture, packaging, or distribution of the investigational product.

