##### **4.2.2.1. On-Treatment Adherence**

The level of on-treatment adherence to the study drug regimen will be determined by the total amount of study drug administered relative to the total amount of study drug expected to be administered during a subject's actual on-treatment period based on the study drug regimen.

The level of on-treatment adherence will be expressed as a percentage using the following formula:

$$\text{On-Treatment Adherence (\%)} = \left( \frac{\text{Total Amount of Study Drug Administered}}{\text{Study Drug Expected to be Administered on Treatment}} \right) \times 100$$

Descriptive statistics for the level of on-treatment adherence with the number and percentage of subjects belonging to adherence categories (eg, < 80%, ≥ 80% to < 90%, ≥ 90% to <120, ≥120) will be provided by treatment group for the Safety Analysis Set.

No formal statistical testing is planned.

A by-subject listing of study drug administration and drug accountability will be provided by subject ID number (in ascending order) and visit (in chronological order).

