	Appendix 7	Added appendix for determining missing and virtual visits due to COVID-19	To provide details of the determination algorithm
	Global	Administrative and editorial changes have been made throughout the SAP, where appropriate	To improve clarity and consistency
Version 1.0 (07 February 2022)	3.8.3	Added the data handling rule for shift tables in safety endpoints	To use a conservative rule for shift tables in safety endpoints
	4.1	Added key study dates table	To provide information for the clinical study report
	4.5	Added overall assessment of COVID-19 impact	To address the overall COVID-19 impact at subject level
	5.2	Added summary of each abdominal pain subscore	To better assess the baseline characteristics of the analysis population
	5.2	Added the number of available segments with SES-CD score for Maintenance study	In response to comments from FDA
	6.2.4	Added summary of the number of available segments with SES-CD score at Induction baseline and post Induction baseline, and change from Induction baseline	In response to comments from FDA
	6.2.5	Added tipping point analysis as a sensitivity analysis for the primary endpoints	To assess the robustness of analysis result under the MNAR (missing not at random) assumption.
	CCI	CCI	CCI
	Appendix 8	Added the SAS programming for the tipping point analysis for binary endpoint	To provide clear guidance on the tipping point analysis
	Global	Editorial changes or clarification languages have been provided throughout the SAP, where appropriate	To improve clarity and consistency
Version 2.0 (xx January 2022)	Global	This SAP is a combination of the SAP for submission within EU and the SAP for submission outside EU. Objectives for both regions and corresponding analyses methods are combined in this SAP	To have one SAP covering all regions
	3.4 and 6.2.7	Add subgroups for key secondary endpoints in addition to the co-primary endpoints	To further explore consistency of the results

Revision Date (DD MMM YYYY)	Section	Summary of Revision	Reason for Revision
	3.8.2	Gaps between analyses visit windows were removed by extending the windows	To make sure all data is included in the analyses
	4.2.1	Improved on the calculation of extent of exposure	To cover all possible scenarios of (partially) missing data
	4.2.2	Modified the calculation of treatment adherence + modified the treatment adherence categories	To be able to summarize overdoses

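### Counting unreturned bottles as fully taken puts early stoppers in the ≥120% adherence category by imputation alone, and that category is meant to summarize overdoses

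*SAP*

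**What the plan says.** SAP 4.2.2 works from one tablet total per subject: "The presumed total number of tablets administered to a subject will be determined by the data collected on the drug accountability eCRF", as tablets dispensed minus tablets returned. For a bottle that does not come back, "If the bottle was not returned, it is assumed that the subject took all the study drug tablets from the dispensed bottle", and "The number of tablets returned will be imputed as zero for the given bottle for study drug adherence calculation purpose".

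SAP 4.2.2.1 takes the amount administered "relative to the total amount of study drug expected to be administered during a subject's actual on-treatment period". The example categories are below 80%, 80% to below 90%, 90% to below 120%, and 120% or more. They are tabulated by treatment group in the Safety Analysis Set, with a by-subject accountability listing and no formal test.

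The Version 2.0 entry for Section 4.2.2 in the SAP revision log (Section 12) explains the change to the calculation and categories: "To be able to summarize overdoses".

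Protocol 7.7.1 says of accountability gaps: "Overdose cannot be established when the subject cannot account for the discrepancy". It makes one exception, where the investigator has reason to suspect that the extra doses were taken. Protocol 5.6 requires all dispensed drug, used or unused, to be returned.

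**The concern.** The numerator and denominator respond to different things. Non-return raises the numerator to the full content of the bottle, while early stopping shortens the denominator. When both happen in one subject, the ratio exceeds 100% however the subject took the drug. The ≥120% category then mixes people who may have taken too much with people who stopped and kept a bottle, and the table cannot separate them.

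The same rule errs in the other direction for a subject who takes few tablets and loses the bottles: the shortfall disappears. Since protocol 5.6 requires return, a missing bottle is missing data rather than evidence of intake.

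At stake are the adherence summary for 200 mg, 100 mg and placebo, and any statement about overdose that the study report draws from its top category.

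**Working it through.** The documents give no adherence figure to reproduce, so this applies the SAP formula to simple cases.

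**Inputs**
- Two tablets a day in every arm (protocol 5.3).
- Bottle content: "Each bottle contains 30 tablets" (protocol 5.2.2).
- Dispensing on Day 1 and at Weeks 4, 11, 14, 20, 26, 34, 42 and 50 (protocol Appendix 2).
- Bottles per visit are not stated. Assumption: the fewest that reach the next dispensing. The 28 days from Day 1 to Week 4 need one of each type (60 tablets). The 49 days from Week 4 to Week 11, and the 42 days from Week 14 to Week 20, need two of each type (120 tablets).

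**Formula:** adherence = (dispensed − returned) / (2 × days on treatment), with returned = 0 for a kept bottle.

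| Case | Calculation | SAP score | Actual intake |
|---|---|---|---|
| Both Day 1 bottles kept, stop Day 10 | 60/20 | 300% | 100% if all doses taken |
| Same, stop Day 25 | 60/50 | 120% | as above |
| Same, stop Day 28 | 60/56 | 107% | as above |
| Full intake to Day 28, Week 4 supply kept, stop Day 35 | (56+120)/70 | 251% | 100% |
| Same, stop Day 73 | 176/146 | 120.5% | 100% |
| Maintenance, Week 14 supply kept, stop 7 days later | (42+120)/56 | 289% | 100% |
| Full intake to Day 28, half of the 98 tablets due by Day 77 taken, Week 4 supply lost | (56+120)/154 | 114% | (56+49)/154 = 68% |

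So every stop up to Day 25 with both Day 1 bottles kept lands in ≥120%, as does every stop up to Day 73 with the Week 4 supply kept.

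**Sensitivity to the bottle assumption.** With only one bottle of each type at Week 4, the Day 35 stop gives (56+60)/70 = 166%, and the score stays at ≥120% up to Day 48 (116/96 = 121%). With just one of the two Day 1 bottles kept and the other counted correctly, the score is ≥120% up to Day 21 ((30+21)/42 = 121%). The threshold day moves; the direction does not.

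**Later in Maintenance the excess shrinks.** After 105 days of full intake with the Week 26 supply kept (two of each type), a stop 7 days later gives (210+120)/224 = 147%, and a stop 42 days later gives 330/294 = 112%.

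**Under a cap** at the tablets expected to the next dispensing or last dose, the Day 10 case becomes 20/20 = 100%, the Day 35 case (56+14)/70 = 100%, and the poor taker (56+98)/154 = 100%. Treating kept bottles as unknown gives bounds of 0% to 300%, 80% (56/70) to 251%, and 36% (56/154) to 114%. The poor taker's true 68% lies inside the last pair.

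**Pooling of bottle types.** With all bottles returned and dummy intake at 100%, the pooled score is (active + 100%)/2: 80% active intake shows as 90%, and 0% shows as 50%.

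**The case against.** Adherence feeds no test, estimand or analysis set, and the SAP itself calls the tablet count presumed. SAP 4.2.2 and 4.2.2.1 never use the word overdose. The link comes only from the reason given in the revision log, which covers the calculation and categories together, and protocol 7.7.1 concerns special-situation reporting and carries the investigator exception. Withdrawing subjects should attend an early termination visit and a visit 30 days after the last dose, so there are two occasions to recover bottles. If the last dose date is missing, SAP 4.2.1 imputes a later contact or disposition date, which can lengthen the denominator. Exposure by dates, the accountability and kit listings, and the summary of major deviations let a reader trace an odd individual value.

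Most of this stands, and it limits the weight of the point. It does not remove it. The listings explain single subjects but do not correct the table or count unreturned bottles. The revision log gives the sponsor's own purpose for the calculation, and the imputation defeats that purpose.

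Two stronger readings are tempting. A reader might infer that missed active doses are hidden. That the tablet count pools active and dummy is itself an inference: the SAP gives one total without a split, and a milligram reading would be 0/0 on placebo. With bottles returned, pooling halves an active shortfall rather than concealing it, and a subject who never takes the active tablet still scores 50%, in the below-80% category. A reader might also infer that non-return differs by arm and biases the comparison of doses. The documents give no discontinuation or bottle-return rates to support that.

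**Conclusion.** The point holds for the descriptive adherence table and any apparent-overdose count read from it. For an early stopper who keeps bottles, ≥120% can arise from the imputation alone: 300% for a Day 10 stop, about 251% for a Day 35 stop. A poor taker who loses bottles is scored as adherent, at 114% against 68%. These figures rest on two tablets a day, 30 per bottle and the assumed minimum number of bottles per visit. The effect requires stopping well before the supply runs out: a Day 28 stop with both first bottles kept, or an Induction completer with the Week 4 supply kept, stays below 120%. How many subjects would be affected cannot be estimated from the documents. Efficacy conclusions are untouched.

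The conflict with protocol 7.7.1 is one of use: that section would not let these subjects be called overdosed unless the investigator suspected extra intake, while the SAP's stated purpose invites that reading.

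**What to change.** In SAP 4.2.2:

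- Cap the tablets credited for an unreturned bottle at the number expected up to the next dispensing or the last dose, whichever is earlier, less what returned bottles from the same dispensing already account for.
- Add a sensitivity summary that treats unreturned bottles as missing, with bounds from none to all taken. Leaving the affected intervals out altogether is less suitable as the main rule, because it drops data informatively and leaves some subjects with no value.
- Report the number of subjects and bottles not returned, by arm.
- State that ≥120% is not an overdose determination and that overdose is defined as in protocol 7.7.1. Before planning a table of overdoses from special-situation reports, confirm that those forms reach the clinical database; the documents do not show this.
- If the accountability data identify bottle type, also report adherence by type. The SAP lists kit IDs but does not say that they separate active from dummy.

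The cost is SAP wording and modest programming. The cap, bounds and counts use accountability data already collected, and trial conduct does not change. The downside is that the cap can still overstate a poor taker (100% against 68% in the example), which the bounds make visible.

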##### **4.2.2.1. On-Treatment Adherence**

The level of on-treatment adherence to the study drug regimen will be determined by the total amount of study drug administered relative to the total amount of study drug expected to be administered during a subject's actual on-treatment period based on the study drug regimen.

The level of on-treatment adherence will be expressed as a percentage using the following formula:

$$\text{On-Treatment Adherence (\%)} = \left( \frac{\text{Total Amount of Study Drug Administered}}{\text{Study Drug Expected to be Administered on Treatment}} \right) \times 100$$

Descriptive statistics for the level of on-treatment adherence with the number and percentage of subjects belonging to adherence categories (eg, < 80%, ≥ 80% to < 90%, ≥ 90% to <120, ≥120) will be provided by treatment group for the Safety Analysis Set.

No formal statistical testing is planned.

A by-subject listing of study drug administration and drug accountability will be provided by subject ID number (in ascending order) and visit (in chronological order).

### **4.3. Protocol Deviations**

Subjects who did not meet the eligibility criteria for study entry, but enrolled in the study will be summarized. The summary will present the number and percentage of subjects who did not meet at least 1 eligibility criterion and the number of subjects who did not meet specific criteria by treatment group and overall based on the All Randomized Analysis Set. A by-subject listing will be provided for those subjects who did not meet at least 1 eligibility (inclusion or exclusion) criterion. The listing will present the eligibility criterion (or criteria if more than 1 deviation) that subjects did not meet and related comments, if collected.

Protocol deviations occurring after subjects entered the study are documented during routine monitoring. The number and percentage of subjects with major protocol deviations by deviation reason (eg, nonadherence to study drug, violation of key inclusion/exclusion criteria) will be summarized by treatment group and overall for the All Randomized Analysis Set for each individual study. A by-subject listing will be provided for those subjects with any major protocol deviation.

Similar summary and listing will be provided for major protocol deviations due to COVID-19.

### **4.4. Missed and Virtual Visits due to COVID-19**

A summary of subjects with missed or virtual visits due to the COVID-19 pandemic will be provided for each scheduled study visit by treatment group and overall for the All Randomized Analysis Set for each individual study. For each visit, the summary will present the number and percentage of subjects who missed the visit due to COVID-19 or had a virtual visit due to COVID-19.

An overall summary of the number and percentage of subjects with missed or virtual visits (eg, subjects with at least 1 missed or virtual visit, subjects with 1, 2, 3, or > 3 missed or virtual visits) due to the COVID-19 pandemic will be provided by treatment group and overall.

A by-subject listing of subjects with missed or virtual visits due to COVID-19 will be provided by subject ID number in ascending order.

Information regarding missed or virtual visits due to COVID-19 was collected as free text in the CRF comment fields. The determination of missing or virtual visits due to COVID-19 was done using Natural Language Processing (NLP) to search the CRF comment fields. A detailed explanation of the algorithm is given in [Appendix 7](#).

